1.3.2 Benefit-Risk Assessment

1.3.2.1 Treatment in Combination with Oseltamivir

All patients in the study will receive the current SOC treatment of oseltamivir either with or without MHAA4549A. Therefore, all patients at minimum will be treated with SOC for influenza. Given that MHAA4549A is an antibody, the potential for interaction with oseltamivir is very low. In the ongoing Phase 2a challenge study (GV28985), several study subjects received MHAA4549A followed by oseltamivir with no AEs attributable to the combination therapy noted to date. In addition, the PK profile of oseltamivir in concomitantly treated subjects will be assessed.

1.3.2.2 Drug Mechanism and Preclinical Studies

The available pre-clinical data suggest that there is low risk for drug target-related safety events in healthy humans since MHAA4549A specifically targets an epitope on a viral protein (i.e., the human influenza A virus hemagglutinin glycoprotein), which is not endogenously expressed in human tissues. Furthermore, there were no adverse MHAA4549A-related findings demonstrated in nonclinical studies at doses up to 150 mg/kg administered weekly for 5 weeks and no evidence of target present in host tissues.

1.3.2.3 Rationale for Selection of Phase 2b Study Population

The target patient population of hospitalized patients with severe influenza A requiring oxygen (O₂) or positive pressure ventilation (PPV) is considered an appropriate population to test MHAA4549A for the following reasons:

- Nonclinical safety data does not show any expected or unexpected toxicity.
- Clinical safety data for MHAA4549A demonstrates a well-tolerated safety profile. There were mild, related AEs observed in the Phase 1 study (GV28916) and MHAA4549A was well tolerated. No ATAs were detected. Safety data from the ongoing Phase 2a challenge study (GV28985) was observed to have mild and moderate transient elevations in alanine transaminase (ALT), aspartate transaminase (AST), and amylase that may be related to either MHAA4549A or to influenza infection. There was no dose-dependent relationship of LFT elevations with MHAA4549A and the overall event rate was in line with that of previous

challenge studies (27/100 [27%] in the study vs. approximately 26%) (Polakos 2006). No SAEs that were related to study drug were observed. Testing for ATAs in Study GV28985 has not yet been concluded.

- The Phase 2a challenge study (GV28985) interim efficacy data demonstrated a significant decrease in viral shedding in the upper respiratory tract at the 3600 mg dose. There was a 97.5% ($p=0.0092$) decrease in the area under viral load–time curve (AUEC) and a 77% ($p=0.0054$) decrease in peak viral load by qPCR measurement in comparison to the placebo group, thus confirming proof of antiviral activity at the 3600 mg dose level.

1.3.2.4 Patient Monitoring and Supervision

MHAA4549A will be administered to enrolled patients in a hospital environment under close medical supervision by physician investigators. Medical staff will be available for prompt evaluation and treatment of any adverse events. Emergency resuscitation equipment and emergency facilities will be readily available. Patients will undergo screening assessments to confirm eligibility, will be closely monitored during the administration of MHAA4549A, and will be resident for at least 24 hours following the administration of MHAA4549A. Furthermore, safety laboratory tests relating to the blood chemistries, including liver function tests, will be conducted.

An independent Data Monitoring Committee (iDMC) will evaluate the safety of MHAA4549A at a timepoint to be specified in the iDMC charter.

The 120-day follow-up period in the Phase 1 and 2a studies allowed for monitoring of subjects for approximately 5 half-lives of the study drug. No ATAs were detected in the Phase 1 study, and the ATA testing for the Phase 2a study is ongoing. The Phase 2b study will also include an appropriate safety follow-up period of up to 30 days and an unlimited collection of all SAEs believed related to MHAA4549A.

Based on the above data and design of this study, the Sponsor concludes that the benefit–risk profile of MHAA4549A in the population with severe influenza is favorable.

2. OBJECTIVES

2.1 SAFETY OBJECTIVES

The safety objectives for this study are as follows:

- To evaluate the safety of MHAA4549A in combination with oseltamivir compared with placebo and oseltamivir in patients with severe influenza A, focusing on the nature, frequency, and severity of serious and non-serious adverse events as well as effects on laboratory values, vital signs, electrocardiogram (ECG) parameters, ATAs, or other safety biomarkers

2.2 PRIMARY EFFICACY OBJECTIVES

The primary efficacy objective for this study is as follows:

- To determine the time to normalization of respiratory function of patients dosed with MHAA4549A in combination with oseltamivir compared to patients dosed with placebo and oseltamivir.

2.3 SECONDARY EFFICACY OBJECTIVES

The secondary efficacy objectives for this study are as follows:

- To measure clinical failure, as defined in Section 3.3.3, after 24 hours post-infusion of study drug
- To determine the time to clinical resolution of vital signs
- To measure mortality in patients
- To determine changes in the extent and duration of viral shedding in upper respiratory samples
- To measure the duration of hospital and/or ICU stay
- To measure antibiotic usage for respiratory indications
- To measure the frequency and severity of the following secondary complications of influenza:
 - Pneumonia (hospital acquired pneumonia [HAP]/ ventilator acquired pneumonia [VAP])
 - Exacerbations of chronic lung disease
 - Myocarditis
 - Acute respiratory distress syndrome (ARDS)
 - Otitis media
 - Other related complications
 - Readmission rates at 30 days after study treatment
- To measure duration of PPV
- To measure readmission rates

2.4 PHARMACOKINETIC OBJECTIVES

The major PK objective for this study is as follows:

- To characterize the PK profile of MHAA4549A in serum

The exploratory PK objectives for this study are as follows:

- [REDACTED]
- [REDACTED]

2.5 EXPLORATORY OBJECTIVES

The exploratory objectives of this study are as follows:

- █ [REDACTED]
- █ [REDACTED]
- █ [REDACTED]
- █ [REDACTED]
- █ [REDACTED]
- █ [REDACTED]
- █ [REDACTED]

3. STUDY DESIGN

3.1 DESCRIPTION OF THE STUDY

3.1.1 Overview of Study Design

This is a Phase 2b, randomized, double-blind, placebo-controlled study designed to assess the safety and clinical activity of a single intravenous (IV) dose of MHAA4549A in hospitalized patients with severe influenza A in combination with oseltamivir versus a comparator arm of placebo with oseltamivir. This study is planned to take place in approximately 170 study centers globally.

Patients will be randomized 1:1 into two treatment groups: a single IV dose of 3600 mg of MHAA4549A with oseltamivir or a single IV dose of placebo with oseltamivir. All patients will receive oseltamivir, a NAI, as standard therapy for a minimum of 5 days after study drug administration. Oseltamivir at doses of 75 BID or 150 mg BID is permitted in order to be consistent with local SOC practice. Treatment for longer than 5 days is permitted based on local investigator discretion. The patient must start Sponsor-supplied oseltamivir within 8 hours of study drug administration. The study has a planned enrollment of approximately 334 patients globally.

Hospitalized patients with an O₂ or PPV requirement will be evaluated for influenza A infection. Enrollment in this study requires ongoing treatment within 24 hours of hospital admission with one of the following:

- any PPV or
- any supplemental O₂ to maintain oxygen saturation (SpO₂) >92% (see Section 3.3.2)

Patients on PPV should not exceed 45% of the total patients enrolled.

A Sponsor-supplied rapid influenza test and/or a local polymerase chain reaction (PCR) test must be used as an aid in the diagnosis of influenza A infection.

[REDACTED]

[figure not shown]
At the time of randomization, patients who are eligible for enrollment as described above, will be randomized to receive MHAA4549A at a dose of 3600 mg or placebo. Patients will be stratified by country, PPV versus supplemental O₂ on the day of admission, and suspected or confirmed bacterial pneumonia versus no bacterial pneumonia based on the status on the day of admission.

Eligible patients who are enrolled into the study will receive either a single IV infusion of MHAA4549A or a single IV infusion of placebo on Day 1. All patients must have the study drug infused within 48 hours of hospital admission or sooner if possible. All patients will receive oseltamivir for a minimum of 5 days (10 doses), starting on Day 1, beginning no later than 8 hours after study drug administration.

All patients will be followed and evaluated at minimum on a daily basis for the duration of their hospital stay consistent with the planned schedule of assessments. Any suspicion of bacterial superinfection should be thoroughly evaluated including microbiological confirmation, if possible. A follow-up study visit should occur on Day 14 ± 1 (if discharged before Day 14) and Day 30 ± 4 days, if discharged before Day 30.

A schedule of assessments is provided in [Appendix 1a](#) and [Appendix 1b](#). A diagram of the study design is presented in [Figure 1](#).

Figure 1 Phase 2b Study Design (GV29216)

*Oxygen requirement = on ventilation or supplemental oxygen to maintain oxygen saturation >92%
 **Quidel Sofia rapid antigen test and/or PCR assay must be used as an aid in the diagnosis of influenza A

3.1.2 Independent Data Monitoring Committee

An iDMC, which consists of two independent physicians and one independent biostatistician, will review safety data of the trial to ensure the safety of the patients enrolled. This should allow early detection of any potential safety concern and, thus, ensure the best possible protection of patients’ safety. In addition, it includes a non-voting biostatistician from an independent data coordinating center (IDCC) who prepares the safety reports, including information on patient accrual and SAEs from the study. The iDMC reviews the safety reports, addresses any safety concerns, and informs the Sponsor whether or not to continue the study.

A detailed description of the procedures, data flow, and meeting schedule of the iDMC will be provided in a separate iDMC charter.

3.1.3 End of Study

The end of study is defined as the first day when all patients have had a study completion visit or early termination visit or have otherwise been discontinued from the study.

3.2 RATIONALE FOR STUDY DESIGN

3.2.1 Rationale for Study Design

Hospitalized influenza A infection represents a high unmet need, which, when left untreated, may progress to a more serious disease that may result in significant morbidity and mortality in otherwise healthy adults as well as in vulnerable populations.

This study is designed to estimate the improvement in outcome of a combination regimen of MHAA4549A with oseltamivir compared to a SOC arm of placebo with

oseltamivir. The study population will include hospitalized patients with influenza A requiring O₂ support and/or PPV support within 24 hours of hospital admission.

Study GV29216 will be a Phase 2b study involving approximately 334 patients. The sample size was determined based on an expected clinically meaningful difference of 1–2 days improvement in time to normalization of respiratory function between the control and treatment arms, assuming a 5-day median time to the time to normalization of respiratory function in the SOC arm ([Blackwood 2011](#); [PREMIER® database](#)).

This design ensures that all patients in the trial will receive the current NAI treatment, oseltamivir, as SOC at a minimum, and will evaluate the clinical benefit of combining MHAA4549A with this SOC regimen. Therefore, this study aims to identify a regimen that could deliver maximum benefit in this high unmet need disease, while still treating all enrolled patients with the currently accepted SOC.

3.2.2 Rationale for Patient Population and Primary Endpoint

Severe influenza, for the purpose of this study, is defined as requiring one of the following treatments: PPV or any supplemental O₂ to maintain an SpO₂ > 92%. PPV is defined as any mechanical positive pressure device to maintain oxygenation; this can include mask ventilation and intubation. A Sponsor-supplied rapid influenza test and/or a local PCR must be used as an aid in the diagnosis of influenza A infection.

This patient population was chosen based on the rationale that respiratory failure is a hallmark of influenza and a major driver of morbidity and mortality, as well as hospitalization. The recovery from ventilator support has been shown to be directly proportional to time spent in the ICU ([Blackwood 2011](#); [PREMIER® database](#)). Based upon an analysis of morbidity and mortality, the patient population that requires supplemental O₂ or ventilation on their first day of admission was determined to have a high unmet medical need as they have an estimated mortality of 9%–32%, and 27% require admission to the ICU, according to analysis of a database of over 70,000 hospitalized patients in the US from 2005–2012 ([PREMIER® database](#)).

Support for use of the respiratory endpoint in this population comes from recently published data demonstrating that a composite endpoint that captured respiratory rate, fever, heart rate, and blood pressure resolution was primarily driven by the respiratory component of the endpoint ([Marty et al. 2014](#)).

3.2.3 Rationale for Control Group and Treatment Window

In this study, the SOC regimen for the control or comparator group is oseltamivir, an NAI. In the treatment groups, MHAA4549A will be dosed in addition to an oseltamivir SOC regimen. The oseltamivir dose will be consistent with the local investigator practice at each site where the study will be conducted. Either 75 mg or 150 mg orally BID oseltamivir for a minimum of 5 days is permitted following treatment with MHAA4549A. Treatment for longer than 5 days is permitted based on local investigator discretion. The

oseltamivir dosing regimen, including the renal dosing adjustment, is listed in [Table 2](#). This control treatment was based on consideration of safety, ethics, and efficacy for treatment of severe influenza and is consistent with guidelines for antiviral treatment of hospitalized patients with influenza ([Harper et al. 2009](#), [Fiore 2011](#)).

Table 2 Oseltamivir Dosing Regimen

Neuraminidase Inhibitor	Dosing Regimen	Duration of Therapy
Oseltamivir	75 mg or 150 mg orally BID ^a 75 mg oral once daily for adult patients with creatinine clearance (CrCL) between 10 and 30 mL/min ^b	5 days ^c

^a 75 mg or 150 mg dose at the discretion of the investigator, and dose must be documented. Capsules can be opened and the granules administered via nasogastric tube, if required.

^b No recommended dosing regimens are available for patients with end-stage renal disease undergoing routine hemodialysis or continuous peritoneal dialysis treatment.

^c Longer treatment times are at the discretion of the investigator.

From a safety standpoint there are no expected drug interactions between MHAA4549A, a monoclonal antibody, and any NAI, which are small molecule drugs that bind to a different viral protein than MHAA4549A. In the Phase 2a challenge study, all subjects that were dosed with MHAA4549A also received a 5-day course of oseltamivir starting on Day 7. There were no safety effects attributable to the combination when the drugs were present concurrently. The pharmacokinetics of oseltamivir and its potential interaction with MHAA4549A are being assessed from this Phase 2a.

For this Phase 2b study, a combination of MHAA4549A and oseltamivir was determined to be the most clinically feasible treatment regimen, both from an ethical as well as a practical perspective. The treatment of all patients with oseltamivir ensures that all patients will receive SOC given the high morbidity and mortality of hospitalized patients with influenza A along with guidelines from Centers for Disease Control and Prevention (CDC) and Infectious Diseases Society of America (IDSA) stating NAIs are the SOC for hospitalized patients with influenza A ([Harper et al. 2009](#) and [CDC Website](#)). Further, pre-clinical efficacy data from a study using MHAA4549A and oseltamivir in combination, showed a potential synergistic effect of both compounds which may be due to the different and potentially complementary mechanisms of action, i.e. targeting viral hemagglutinin and neuraminidase.

Dosing of MHAA4549A is confined to a treatment window designed for best expected treatment success and to ensure that any observed effects can be attributed to the study drug with high confidence. MHAA4549A shall only be dosed within 5 days of symptom onset, within 3 days of initial treatment with a NAI, and no later than 48 hours after admission to the hospital. This proposed window is supported by data demonstrating

that hospitalized influenza patients benefit from NAI treatment even at 5 days from symptom onset (Louie et al. 2012).

3.2.4 Rationale for MHAA4549A Dosage

[figure not shown]
A single IV dose of 3600 mg of MHAA4549A was selected to assess the efficacy of MHAA4549A and to provide data for further clinical development. The selection of dose in this study for severely ill patients was based on the observed human pharmacokinetics in Phase 1 and the relationship between the pharmacokinetics, pharmacodynamics, and efficacy observed in a Phase 2a human challenge model of influenza. The dose is adequately supported by safety data from the completed Phase 1 study and ongoing Phase 2a study in healthy volunteers, which has completed dosing. MHAA4549A was shown to be safe and well-tolerated at all dose levels (ranging from 1.5 mg/kg to 45 mg/kg for Phase 1 and 400-3600 mg for Phase 2a) through a follow-up period of 120 days post-dose in the Phase 1 study. The dose level used in this study was determined following an interim analysis of the 1200-mg and 3600-mg doses in the Phase 2a study, GV28985, which demonstrated the following:

- The 3600-mg dose demonstrated a significant decrease in viral shedding in upper respiratory samples. Based on current interim analysis data, there was a 97.5% ($p=0.0092$) decrease in AUEC and a 77.3% decrease in peak viral load by qPCR measurement compared to the placebo group.
- The 1200-mg dose level was not efficacious.
- There are no safety concerns at the 3600-mg dose level to date.
- Hospitalized patients generally have a longer duration of viral shedding and significantly more viral burden in the lower lung compartments; therefore, high concentrations of mAb are likely needed to achieve sufficient occupancy of the virus binding sites in the upper and lower respiratory compartments. Furthermore, higher concentrations of mAb are necessary to mitigate the risk of resistance for MHAA4549A and neuraminidase inhibitors such as oseltamivir.

The Phase 1 study was conducted using body-weight based dosing followed by a fixed dosing strategy that was used in the Phase 2 study. Thus, the fixed dosing regimen that was used in the Phase 2a study will be used for this study, given the practical advantages and positive safety profile of MHAA4549A to date. Further, fixed dosing is generally recommended with monoclonal antibodies, due to their minimal PK variability (Bai et al. 2012). The PK variability introduced by different dosing regimens (i.e., body-weight based dosing versus fixed dosing) is moderate relative to the variability generally observed in pharmacodynamics, efficacy, and safety and would not be expected to be clinically meaningful.

3.2.5 Rationale for Biomarker Assessments

[REDACTED]

3.3 OUTCOME MEASURES

3.3.1 Safety Outcome Measures

The safety outcome measures for this study are as follows:

- Adverse events and clinical laboratory abnormalities
- Vital signs, physical findings, ATAs, and clinical laboratory results during and following administration of MHAA4549A

3.3.2 Primary Efficacy Outcome Measure

The primary outcome measure for this study is as follows:

- Time to normalization of respiratory function defined as:
 - The time to cessation of O₂ support resulting in a stable SpO₂ >95% for at least 24 hours (see [Appendix 2](#) for details)

3.3.3 Secondary Efficacy Outcome Measures

The secondary efficacy outcome measures for this study are as follows:

- Clinical failure 24 hours post-infusion of study drug; defined as:
 - Progression to increased O₂ requirement defined by an increase in oxygen supplementation from low flow oxygen (2–6 L/min) to high flow oxygen (>6 L/min) or from oxygen supplementation alone to any PPV
 - Progression to ICU
 - Prolonged ventilation or O₂ support defined by >2 weeks, or
 - Death
- Time to clinical normalization of vital signs (3/5 criteria must be met):
 - SpO₂ > 95% without supplemental O₂ for at least 24 hours
 - Respiratory rate < 24 without supplemental O₂ for at least 24 hours
 - Core temperature < 37.2°C immediately prior to receipt of any antipyretic drug, and at least 6-8 hours from the last dose of antipyretic or core temperature >36°C in patients who are initially hypothermic
 - Heart rate (HR) < 100/minute
 - Systolic blood pressure (SBP) > 90 mmHg

- All-cause mortality at Day 14 and Day 30
- Influenza A viral load in nasopharyngeal samples
 - AUEC
 - Peak viral load
 - Time to resolution of infection
- Duration of hospitalization
- Duration of ICU stay
- Antibiotic usage for respiratory infections
- Complications of influenza:
 - Pneumonia (HAP/VAP)
 - Exacerbations of chronic lung disease
 - Myocarditis
 - ARDS
 - Otitis media
 - Other related complications
- All-cause readmission at Day 30
- Duration of ventilation

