4.6.6 Vital Signs

Vital signs will include measurements of resting SpO₂ (see Section 4.6.7 for measurement), respiratory rate, pulse rate, temperature, and systolic and diastolic blood pressures after the patient has been in a seated or supine position for at least 10 minutes. Patients in intensive care may have vital signs assessed following local procedures, but those procedures should be captured in the eCRF in accordance with the eCRF instructions.

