6.4.2 Secondary Efficacy Endpoints

- Proportion of patients with clinical failure 24 hours post-infusion of study drug
- Median time to clinical resolution of vital signs
- Hazard ratio for mortality at Day 14 and Day 30
- Mean and median AUC of viral load
- Mean and median peak viral load
- Median duration of viral shedding in upper respiratory samples
- Median duration of hospitalization
- Median duration of ICU stay
- Proportion of patients requiring antibiotics for respiratory indications during study
- Proportion of patients with influenza secondary complications
- Median duration of ventilation
- Proportion of patients who are readmitted by Day 30

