APPENDIX 1b Schedule of Assessments: Follow-Up Period

- If a patient is discharged prior to Day 14, he/she will need to complete the following assessments for Day 14 and Day 30 below.
- If a patient is discharged prior to Day 30 and after Day 14, he/she will need to complete the following assessments for Day 30 below.
- If patient is hospitalized for Day 14, and/or Day 30, please refer to [Appendix 1a](#).

Day (D)	D14 ± 1 (If Discharged BEFORE D14)	D30 ± 4 (Study Completion) or Early Discontinuation
Concomitant medications ^a	x	x
Vital signs ^b	x	x
Electrocardiogram (12-lead) ^c	x	x
Weight & height, BMI ^d	x	x
Adverse events	x	x
Hematology ^e	x	x
Chemistry 20 panel ^e	x	x
Coagulation panel ^e	x	x
Urinalysis ^e	x	x
Flu antibodies (HAI)	x	x
████████████████████		x
Serum for MHAA4549A PK measurements ^f	x	x
████████████████████	x	x
████████████████████	x	x
███████████		x
███████████		x
███████████		x
███████████		x

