6.4.2 Secondary Efficacy Endpoints

- Proportion of patients with clinical failure after 24 hours post-infusion of study drug
- Median time to clinical resolution of vital signs
- Hazard ratio for mortality at Day 14, Day 30, and Day 60
- Mean and median AUC of viral load
- Mean and median peak viral load
- Median duration of viral shedding in upper respiratory samples
- Median duration of hospitalization
- Median duration of ICU stay
- Proportion of patients requiring antibiotics for respiratory indications during study

- Proportion of patients with influenza secondary complications
- Median duration of ventilation
- Proportion of patients who are readmitted by Day 30 and Day 60

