APPENDIX 1a Schedule of Assessments: Hospitalization Days

Notes: Unless otherwise indicated, all assessments on Day 1 should be performed prior to study drug administration; x's within parentheses, i.e., (x), indicate optional assessments. Please refer to Follow-up Period table for visits to be completed after patient is discharged from hospital prior to Day 60.

Day (D)	Screening	Hospitalized Days (only to be completed while patients are hospitalized)														Hospital Discharge ^a	D30	D60 Study Completion or Early Discontinuation while Hospitalized
	D -2,-1	D1 (Randomization)	D2	D3	D4	D5	D6	D7	D8	D9	D10	D14	D20	D25				
Confirm study drug administration can occur within 48 hours of hospital admission																		
Informed consent ^b	x																	
Rapid influenza A test ^c	x																	
Local influenza A PCR test ^d	x																	
Inclusion/exclusion criteria	x																	
Medical history and demographic data	x																	
Confirm onset of flu symptoms (≤ 5 days prior to study drug administration on Day 1)	x																	
Confirm history of baseline SpO ₂ > 92%	x																	
Pregnancy screening ^e	x																	
Confirm O ₂ requirement ^f	x																	
Respiratory Assessment ^g	x	x	x	x	x	x	x	x	x	x	x	x	x	x	x	x	x	
Concomitant medications ^h	x	x	x	x	x	x	x	x	x	x	x	x	x	x	x	x	x	
Vital signs ⁱ		x	x	x	x	x	x	x	x	x	x	x	x	x	x	x	x	
APACHE score ^j		(x ^z)										(x)			(x)	(x)	(x)	
SOFA score ^k		(x ^z)						(x)				(x)			(x)	(x)	(x)	
Electrocardiogram (12-lead) ^l		x				x						x			x	x	x	
Randomization		x																

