APPENDIX 1b Schedule of Assessments: Follow-Up Period

- If a patient is discharged prior to Day 14, he/she will need to complete the following assessments for Day 14, Day 30, and Day 60 below.
- If a patient is discharged prior to Day 30 and after Day 14, he/she will need to complete the following assessments for Day 30 and Day 60 below.
- If a patient is discharged prior to Day 60 but after Day 30, he/she will need to complete the following assessments for Day 60 below.
- If patient is hospitalized for Day 14, Day 30, and/or Day 60, please refer to Appendix 1a.

Day (D)	D14 ± 1 (If discharged BEFORE D14)	D30 ± 4 (If discharged BEFORE D30)	Day 60 ± 4 (Study Completion) or Early Discontinuation
Concomitant medications ^a	x	x	x
Vital signs ^b	x	x	x
Electrocardiogram (12-lead) ^c	x	x	x
Weight & height, BMI ^d	x	x	x
Adverse events	x	x	x
Hematology ^e	x	x	x
Chemistry panel ^e	x	x	x
Coagulation panel ^e	x	x	x
Urinalysis ^e	x	x	x
Flu antibodies (HAI)	x	x	x
████████████████████		x	x
Serum for MHAA4549A PK measurements ^f	x	x	x
████████████████████	x	x	x
████████████████████	x	x	x
██████████		x	x
██████████		x	x
██████████		x	x
██████████		x	x

██████████; ATA = Anti-therapeutic antibodies; BMI = body mass index; D = day; Dx = diagnostics; eCFR = electronic Case Report Form; ECG = electrocardiogram; HAI = hemagglutinin inhibition; ██████████; PD = pharmacodynamics; PK = pharmacokinetic.

^a Concomitant medications should be recorded for 30 days prior to screening, through the study completion/early discontinuation visit. See exclusion criteria in [Section 4.5.2](#) for prohibited therapies.

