APPENDIX 1b (cont'd) Schedule of Assessments: Follow-up Period

- ^b Vital signs include temperature, respiratory rate, heart rate, systolic blood pressure, and diastolic blood pressure. Temperature should be measured using the same methodology throughout the study and should be measured prior to study drug administration of any antipyretic drugs. In patients who have multiple vital signs taken during any day, the most abnormal value should be recorded from that 24-hour period. Temperature, blood pressure, respiratory rate, and heart rate will be completed after the patient has been supine for > 5 minutes.
- ^c ECG should be recorded after the patient has rested in a supine position for 10 minutes.
- ^d Height will be obtained at screening only. Weight will be obtained at all indicated visits. Height and weight will be recorded in meters and kg, respectively.
- ^e Local laboratory measurements should be used.
- ^f PK samples should be drawn from the opposite arm from the one used for drug infusion and must be labeled with the exact time of draw.

APPENDIX 2

Time to Normalization of Respiratory Function

For the purposes of this study, the time to normalization of respiratory function will be defined as the time to removal of the patient from O₂ supplementation in order to maintain an SpO₂ > 95%.

Patients who are on low flow O₂ (2-6L/min) should receive a daily trial off O₂ in the morning between 6 am – 12 pm as described below.

1. Patient should be resting or sitting.
2. Patient should be fitted with pulse oximeter, and their SpO₂ should be checked once while on O₂ and then again 3 – 5 minutes after turning off O₂ supplementation.
3. If the SpO₂ > 95%, then the time and reading should be recorded. Notify the study doctor so that he/she can make a clinical judgment to determine whether the O₂ can be removed.
4. If the patient is off O₂ for 24 hours and his/her reading the subsequent day is >95%, then the endpoint is considered satisfied. The recorded time for the endpoint corresponds with the initial discontinuation of O₂ and reading.

APPENDIX 3

[REDACTED]

[REDACTED]

[REDACTED]

[REDACTED]

APPENDIX 4

[REDACTED]

[REDACTED]

[REDACTED]

[REDACTED]

[REDACTED]

[REDACTED]

[REDACTED]

[REDACTED]

APPENDIX 5

[Redacted]

[Redacted]
[Redacted]
[Redacted]

[Redacted]
[Redacted]

[Redacted]
[Redacted]

[Redacted]

[Redacted] [Redacted]
[Redacted]

[Redacted] [Redacted]

[Redacted] [Redacted]
[Redacted]

[Redacted] [Redacted]
[Redacted]

[Redacted]

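### Support beyond two weeks counts as clinical failure, but no readable follow-up item records O2 or ventilation after discharge, so the component cannot be determined for a patient sent home on O2 before then

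*Combined protocol and SAP*

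**What the plan says.** Section 3.3.3 (Secondary Efficacy Outcome Measures) defines clinical failure by four components: an increased O2 requirement, progression to ICU, "Prolonged ventilation or O₂ support defined by >2 weeks", and death. The third component is worded the same in Versions 1, 2 and 3 and carries no restriction to inpatient support. Section 6.4.2 summarises the endpoint as a binary outcome: "Proportion of patients with clinical failure after 24 hours post-infusion of study drug" in Versions 2 and 3, "Proportion of patients with clinical failure 24 hours post-infusion of study drug" in Version 1.

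The oximetry row (Version 1), renamed Respiratory Assessment in Versions 2 and 3, stands only in Appendix 1a, under the banner "Hospitalized Days (only to be completed while patients are hospitalized". That table has a Hospital Discharge column.

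After discharge, Appendix 1b applies. In Version 1 it reads "If a patient is discharged prior to Day 14, he/she will need to complete the following assessments for Day 14 and Day 30 below"; Versions 2 and 3 add a Day 60 visit. Its readable rows include concomitant medications, vital signs, ECG, weight, adverse events and laboratory tests. None asks about O2 or PPV. Footnote b to the table says "Vital signs include temperature, respiratory rate, heart rate, systolic blood pressure, and diastolic blood pressure", which leaves out SpO2, whereas Section 4.6.6 says "Vital signs will include measurements of resting SpO₂".

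Section 6.4 provides for no imputation apart from censoring in the time-to-event analyses.

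**The concern.** A component defined by duration needs a stop date, or at least a status beyond two weeks. The schedule provides that only for patients who are still inpatients.

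Discharge on O2 before two weeks is possible under the plan. Footnotes to Appendix 1a require residence for only 24 hours after the infusion and foresee discharge by Day 5, and no passage requires O2 to be off at discharge. Section 4.1.2 excludes patients on home or baseline O2, so O2 at discharge would be a new need, which is what this component is meant to count. With about 170 centres worldwide, discharge practice could vary.

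At stake are the level of the failure proportion and the treatment difference on this component. If treatment changes how early patients leave hospital while still on O2, the lost information is not balanced between the arms. Data never collected cannot be recovered at analysis.

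**Working it through.** **Reading the schedules together**

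1. At discharge, Appendix 1a shows who leaves on O2, so these patients can be identified.
2. After discharge, nothing readable in Appendix 1b gives support status or a stop date. Some of its rows are redacted. A respiratory row is unlikely to be among them, because the corresponding row in Appendix 1a is not redacted.
3. The Day 14 ± 1 visit falls close to the two-week mark. Whether it falls before or after depends on whether the two weeks run from the start of O2, from admission (up to 48 hours before infusion) or from infusion. Section 3.3.3 does not say.
4. A patient who also meets the escalation, ICU or death component is a failure regardless. The gap concerns those whose only failure would be prolonged support.

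**Size: illustration for this component only**

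The plan gives no figure for clinical failure, so there is none to reproduce. The check borrows the planning model in Section 6.1: exponential times, control median 5 days, 300 evaluable patients (150 per arm). The model was first checked against Table 7. With a 4-day active median (hazard ratio 0.80) and 30 days of follow-up, expected events are 150 × (1 − 2^(−30/5)) + 150 × (1 − 2^(−30/4)) = 296.8. Power is Φ(½√296.8 × |ln 0.80| − 1.96) = 48.5%; the plan states 48%.

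The share still on support after 14 days is P(T > 14) = 2^(−14/median):

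- control, 5 days: 2^(−2.8) = 0.1436, about 21.5 of 150
- MHAA4549A, 4 days: 2^(−3.5) = 0.0884, about 13.3 of 150
- difference: 0.1436 − 0.0884 = 0.055

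Let s be the share of these patients who go home on O2 before Day 14 and are not seen again for support. The documents give no value, so 10% to 50% is an assumption. For an arm with true proportion p, the observed proportion is p(1 − s) if they are scored as non-failures, and p(1 − s)/(1 − ps) if they are dropped as missing.

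| s, both arms | Scored as non-failures | Dropped as missing |
|---|---|---|
| 0 | 5.5 points | 5.5 points |
| 10% | 5.0 | 5.1 |
| 25% | 4.1 | 4.4 |
| 50% | 2.8 | 3.1 |

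In the 50% row, scored as non-failures: 0.1436 × 0.5 − 0.0884 × 0.5 = 0.028. This is 10.8 control and 6.6 active patients misclassified.

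Unequal shares, scored as non-failures:

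- 50% control, 25% active: 0.1436 × 0.50 − 0.0884 × 0.75 = 0.006, or 0.6 points
- 25% control, 50% active: 0.1436 × 0.75 − 0.0884 × 0.50 = 0.063, or 6.3 points

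**The case against.** A reader might infer that a patient sent home on O2 is scored as a non-failure, so that early discharge on O2 counts as success. The documents do not say this. Section 6.4 rules out imputation, and treating an unknown component as not failed would itself be a form of imputation. The patient could equally be missing, or be judged from other records. What stands is that no rule is given.

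A reader might also infer that support can be recorded only in hospital. That is too absolute. Under Section 4.6.6 a resting SpO2 could be taken with the follow-up vital signs, although footnote b to Appendix 1b conflicts with this. Concomitant medications are collected to study completion (Section 4.5.1), and home O2 might be entered there. Both routes are incidental: a saturation reading gives neither use nor duration, O2 is not named as a medication, and PPV is not one.

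The arithmetic is open to fair criticism. It covers one component rather than the composite, ignores death and the other components, uses the primary-endpoint model as a proxy for duration of support, and rests on assumed home-O2 shares. It shows how the component behaves, not how far the endpoint is biased.

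The setting also limits the weight of the point. This is one component of one secondary endpoint, in a study that plans no formal hypothesis testing (Section 6). Versions 2 and 3 stratify randomization by site, which helps to balance local discharge policy between arms. It does not restore lost failures, nor does it protect against an effect of treatment on discharge timing.

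**Conclusion.** The point holds as a gap in data collection and definition. For a patient discharged on O2 before two weeks who meets no other component, following the plan exactly leaves the prolonged-support component undeterminable. How to classify that patient and when the two weeks begin are both unstated.

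The number of patients affected cannot be derived from the documents. In the illustration, equal losses in the two arms reduce the difference on this component, somewhat less if the patients are dropped than if they are scored as non-failures. Unequal losses can nearly remove the difference or make it larger than the true one, so no single direction of bias can be claimed.

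The schedules and definition were checked in Versions 1 to 3. The supplied text includes neither the body of Version 5 (Global), which adds an 8400 mg arm, nor the separate SAP to which Section 6 defers analysis details. Whether either closes the gap cannot be confirmed here. The point is a cheap improvement and not a threat to the primary analysis.

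**What to change.** - **Appendix 1b:** add one item to each existing follow-up visit: O2 or PPV since discharge (yes/no), whether still in use, and the date stopped.
- **Section 3.3.3:** state when the two-week clock starts and that support after discharge counts.
- **Section 6.4 or the SAP:** where support after discharge is unknown, report the clinical-failure proportion twice, with those patients counted as failures and again as non-failures.

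The cost is one eCRF question at visits already scheduled, plus short additions to the endpoint definition and the analysis text. The downside is that a stop date at home relies on patient recall. The same date would also inform the primary endpoint for patients discharged while still on O2. Nothing in patient management changes.
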